3.3. Other Endpoint(s)

3.3.1. Additional Plasma Pharmacokinetic Parameters

- Additional PF-07081532 Plasma Pharmacokinetic parameters CL/F, V_z/F, T_{max}, t_{1/2} as data permit.
- Additional Unbound PF-07081532 Plasma Pharmacokinetic parameters: CL_u/F, V_{z,u}/F as data permit.

The plasma PK parameters for PF-07081532 in Table 5 will be determined using standard non-compartmental methods:

Table 5. Summary of Additional Plasma PK Parameters of PF-07081532 to be calculated

Parameter	rameter Analysis Scale PF-07081532 20	
CL/F*	ln	D
CL _u /F*	ln	D
Vz/F*	ln	D
Vz,u/F*	ln	D
Tmax	R	D
t _{1/2} *	R	D

^{*=}if data permits. Abbreviations: D = displayed with descriptive statistics as outlined in Table 8 in Section 6.3.1, ln = natural - log transformed, R = raw (untransformed).

The plasma PK parameters for unbound PF-07081532 will be calculated as described in Table 6:

Table 6. Summary of Additional Plasma PK parameters of Unbound PF-07081532 to be calculated

Parameter	Method of Determination	Analysis Scale	PF-07081532 20mg
CL _u /F*	Dose/(AUC _{inf,u})	ln	D
Vz,u/F*	$Dose/(AUC_{inf,u} \times k_{el})$	ln	D

^{*=}if data permits. Abbreviations: D = displayed with descriptive statistics as outlined in Table 8 in Section 6.3.1, ln = natural - log transformed, R = raw (untransformed).

3.3.2. Urine Pharmacokinetic Parameters

PF-07081532 Urine Pharmacokinetic parameters CL_r, Ae₂₄, Ae₂₄%

The urine PK parameters for PF-07081532 in Table 7 will be determined using standard non-compartmental methods:

Table 7. Summary of Urine PK Parameters of PF-07081532 to be calculated

Parameter	meter Analysis Scale PF-07081532	
CL_r	ln	A, D
Ae ₂₄	ln	D
Ae ₂₄ %	ln	D

Abbreviations: D = displayed with descriptive statistics as outlined in Table 8 in Section 6.3.1, ln = natural - log transformed, R = raw (untransformed).

3.3.4. eGFR

For reporting purposes, eGFR will be calculated using the 2021 CKD-Scys formula⁽¹⁾:

2021 CKD-EPI	Scr	Scys	Recommended eGFR Equation
Scr-Scys Combined	(mg/dL)	(mg/L)	
Female	if ≤0.7	if ≤0.8	$eGFR = 130 \times (Scr/0.7)^{-0.219} \times (Scys/0.8)^{-0.323} \times (0.9961)^{Age}$
Female	if ≤0.7	if>0.8	$eGFR = 130 \times (Scr/0.7)^{-0.219} \times (Scys/0.8)^{-0.778} \times (0.9961)^{Age}$
Female	if>0.7	if ≤0.8	$eGFR = 130 \times (Scr/0.7)^{-0.544} \times (Scys/0.8)^{-0.323} \times (0.9961)^{Age}$
Female	if>0.7	if>0.8	$eGFR = 130 \times (Scr/0.7)^{-0.544} \times (Scys/0.8)^{-0.778} \times (0.9961)^{Age}$
Male	if ≤0.9	if ≤0.8	$eGFR = 135 \times (Scr/0.9)^{-0.144} \times (Scys/0.8)^{-0.323} \times (0.9961)^{Age}$
Male	if ≤0.9	if>0.8	$eGFR = 135 \times (Scr/0.9)^{-0.144} \times (Scys/0.8)^{-0.778} \times (0.9961)^{Age}$
Male	if>0.9	if ≤0.8	$eGFR = 135 \times (Scr/0.9)^{-0.544} \times (Scys/0.8)^{-0.323} \times (0.9961)^{Age}$
Male	if >0.9	if>0.8	$eGFR = 135 \times (Scr/0.9)^{-0.544} \times (Scys/0.8)^{-0.778} \times (0.9961)^{Age}$

The alternative equations outlined below may be used for exploratory analyses.

CKD-EPI Scr only equation⁽²⁾:

eGFR (mL/min/1.73m²) = $141 \times \min(\text{Scr}/\kappa, 1)^{\alpha} \times \max(\text{Scr}/\kappa, 1)^{-1.209} \times 0.993^{\text{Age}} \times 1.018$ [if female] \times 1.159 [if black]

where:

- SCr is serum creatinine in mg/dL (based on the standardized assay)
- κ is 0.7 for females and 0.9 for males
- α is -0.329 for females and -0.411 for males
- min indicates the minimum of SCr / κ or 1
- max indicates the maximum of SCr $/\kappa$ or 1

• Age is in years

Cockcroft-Gault equation⁽³⁾:

eGFR (ml/min/1.73 m²)= $[(140\text{-Age}) \times \text{Weight} \times 0.85 \text{ if female}]/(72 \times \text{SCr}) \text{ where:}$

- Age is in years
- Weight is in kg
- SCr is in mg/dl (based on the standardized assay)

Modification of Diet in Renal Disease (MDRD)⁽⁴⁾:

eGFR (ml/min/1.73 m²) =
$$175 \times (SCr)^{-1.154} \times (Age)^{-0.203} \times (0.742 \text{ if female}) \times (1.212 \text{ if black})$$

where:

- Age is in years
- SCr is in mg/dl (based on the standardized assay)

3.4. Baseline Variables

Not Applicable.

3.5. Safety Endpoints

See Section 3.2.

4. ANALYSIS SETS (POPULATIONS FOR ANALYSIS)

Data for all participants will be assessed to determine if participants meet the criteria for inclusion in each analysis population prior to unblinding and releasing the database and classifications will be documented per standard operating procedures.

For purposes of analysis, the following analysis sets are defined:

Participant Analysis Set	Description
Enrolled	"Enrolled" means a participant's, or their legally authorized representative's, agreement to participate in a clinical study following completion of the informed consent process and assignment to study intervention. A participant will be considered enrolled if the informed consent is not withdrawn prior to participating in any study activity after screening. Potential participants who are screened for the purpose of determining eligibility for the study, but do not participate in the study, are not considered enrolled, unless otherwise specified by the protocol.
Safety analysis set	All participants assigned to study intervention and who take at least 1 dose of study intervention.

Participant Analysis Set	Description
PK Concentration Set	The PK concentration population is defined as all participants who received at least 1 dose of PF-07081532 and in whom at least 1 plasma concentration value is reported.
PK Parameter Set	The PK parameter analysis population is defined as all participants who received at least 1 dose of PF-07081532 and have at least 1 of the PK parameters of interest calculated.
CCI	

5. GENERAL METHODOLOGY AND CONVENTIONS

The following group labels (or similar) will be used for tables and figures unless otherwise stated:

Group	Description of Group	Label
1	Normal renal function	Without Renal Impairment
2	Mild renal impairment	Mild Renal Impairment
3	Moderate renal impairment	Moderate Renal Impairment
4	Severe renal impairment	Severe Renal Impairment

5.1. Hypotheses and Decision Rules

There is no statistical hypothesis testing planned for this study and no statistical decision rules will be applied.

5.2. General Methods

5.2.1. Analyses for Continuous Endpoints

Unless otherwise stated, continuous endpoints and relevant safety endpoints will be presented using summary statistics: number of observations, arithmetic mean, standard deviation, median, minimum and maximum values.

5.2.2. Analyses for Categorical Endpoints

Categorical endpoints and relevant safety endpoints will be presented using summary statistics: number of observations, counts and percentages.

5.2.3. One-way Analysis of Variance (ANOVA)

The *one-way analysis of variance (ANOVA)* model will include renal impairment group as a factor.

Estimates of the adjusted means and of the adjusted mean differences (Test - Reference) and corresponding 90% CIs will be obtained from the model. These will be exponentiated to

provide estimates of the ratio of adjusted geometric means (Test/Reference) and 90% CI for the ratios.

Residuals from the models will be examined for normality and the presence of outliers via visual inspection of plots of residuals vs predicted values and normal probability plots of residuals but these will not be included in the clinical study report. If there are major deviations from normality or outliers (where studentized residuals are greater than 3 or less than -3) then the effect of these on the conclusions may be investigated through alternative transformations and/or analyses excluding outliers. Justification for any alternative to the planned analysis will be given in the report of the study if applicable.

Example SAS code is given in Appendix 1.

5.2.4. Linear Regression PK Parameters versus Renal Function

Linear regression may be used to characterize the potential relationship between appropriate PK parameters (eg, CL/F, CL_U/F and CL_r) for PF-07081532 and renal function (eGFR). This will be modelled with eGFR (Day 1) as a continuous explanatory variable with each PK parameter modelled separately. Estimates of the statistical slope and intercept, together with their precision (90% CI), and the coefficient of determination (i.e. R-squared and adj-R-squared) will be obtained from the model. Example SAS code is given in Appendix 1.

Residuals from the models will be examined for normality and the presence of outliers via visual inspection of plots of residuals vs predicted values and normal probability plots of residuals but these will not be included in the clinical study report. If there are major deviations from normality or outliers (where studentized residuals are greater than 3 or less than -3) then the effect of these on the conclusions may be investigated through alternative transformations and/or analyses excluding outliers. Alternative model structure may also be considered. Justification for any alternative to the planned analysis will be given in the report of the study

Additionally, as an exploratory analysis, body weight, gender and age may be explored as an additional covariate in the models, as appropriate. This will be implemented by utilizing a stepwise linear regression approach, with model selection using Akaike's Information Criterion [AIC]). All the above covariates will be considered (renal function will be restricted to always remain in the model) and if the final model selected includes at least one of these additional covariates, this additional model will be reported in addition to the main linear regression above. Example SAS code is given in Appendix 1.

5.3. Methods to Manage Missing Data

For the analysis of safety endpoints, the sponsor data standard rules for imputation will be applied.

CCI

5.3.2. Pharmacokinetic Deviations, Missing Concentrations and Anomalous Values

In summary tables and plots of median/mean profiles, statistics will be calculated having set concentrations to missing if 1 of the following cases is true:

- 1. A concentration has been collected as ND (ie, not done) or NS (ie, no sample),
- 2. A deviation in sampling time is of sufficient concern or a concentration has been flagged anomalous by the pharmacokineticist/clinical team.

Note that summary statistics will not be presented at a particular time point if more than 50% of the data are missing.

5.3.3. Pharmacokinetic Parameters

Actual PK sampling times will be used in the derivation of PK parameters.

If a PK parameter cannot be derived from a participant's concentration data, the parameter will be coded as NC (ie, not calculated). Note that NC values will not be generated beyond the day that a participant discontinues.

In summary tables and statistical analyses, statistics will be calculated by setting NC values to missing; and statistics will be presented for a particular group with ≥ 3 evaluable measurements.

If an individual participant has a known biased estimate of a PK parameter (due for example to an unexpected event such as vomiting before all the compound is adequately absorbed in the body), this will be footnoted in summary tables/figures and will not be included in the calculation of summary statistics or statistical analyses.

6. ANALYSES AND SUMMARIES

Data collected before baseline will only be listed, unless otherwise stated.

Unless otherwise stated, all analyses, summaries and listings will be produced by group (as outlined in Section 5) which would include all 4 groups in the same analysis/output.

6.1. Primary Endpoint(s)

6.1.1. PF-07081532 PK Parameters

· Estimand strategy: Not applicable

Analysis set: PF-07081532 Concentration and Pharmacokinetic Parameter Set

6.1.1.1. Main Analysis

C_{max}, AUC_{inf} (if data permit), AUC_{last}, fu, C_{max,u}, AUC_{inf,u} and AUC_{last,u} will be listed, summarized descriptively and analyzed by group for participants in the PK parameter set (as defined in Section 4). Missing values will be handled as detailed in Section 5.3.

A one-way analysis of variance (ANOVA) described in Section 5.2.3, that includes all 4 groups in the same model, will be used to compare the natural log transformed of C_{max} , AUC_{inf}, AUC_{last}, fu, AUC_{inf,u}, AUC_{last,u}, and $C_{max,u}$ of PF-07081532 separately, for each of the renal impairment groups (Test, Groups 2, 3, 4) to the healthy normal renal function group (Reference, Group 1).

For summary statistics, median or mean plots by sampling time, the nominal PK sampling time will be used. For individual participant plots by time, the actual PK sampling time will be used. The plasma PK parameters of PF-07081532 for each group will be summarized as specified in Table 8. below.

Table 8. Summary statistics to be produced for Plasma PK Parameters of PF-07081532

Parameter	Summary Statistics
C _{max} , AUC _{inf} *, AUC _{last} , fu,	N, arithmetic mean, median, cv%, standard deviation,
AUCinf,u*, AUClast,u, and	minimum, maximum, geometric mean and geometric
$C_{ ext{max}, u}$	cv%.

^{*} if data permits

The following plots will be presented:

Box and whisker plots for individual PK parameters (AUCinf, AUClast, Cmax, fu, AUCinf,u, AUClast,u and Cmax,u)) will be constructed by renal impairment group and overlaid with geometric means.

6.1.1.2. Sensitivity/Supplementary Analyses

Linear regression may be used to characterize the potential relationship between appropriate PK parameters (eg, CL/F, CLu/F and CLr) for PF-07081532 and renal function (eGFR), calculated using the 2021 CKD-EPI Scr-Scys Combined equation given in Section 3.3.4, following the methodology described in Section 5.2.4.

Plots of PK parameters (eg, CL/F, CL_w/F and CL_r) for PF-07081532 versus renal function at baseline (eGFR as obtained on Day 1) will be constructed. A regression line and 90% confidence region for the PK parameters and eGFR will included if appropriate. Vertical lines for the renal function group cut-off values will also be presented on the plots. Different symbols will be used to identify participants from different renal function groups

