- If done around the time of a blood draw, ECG and vital signs should be collected before the blood draw. ECG and vital signs on Day 1 at Time 0H must be done before collection of the pre-dose blood samples. If an IV catheter is utilized for blood sample collections, ECGs and vital sign assessments (BP and pulse rate) should be collected before insertion of the catheter.
- Glucometer measures will be taken before breakfast in participants with T2DM on all days while inpatient. Additional measurements may be made at the discretion of the investigator. ьio
- approximately 0H, 4H, 6H (optional), 10H, 14H (optional) relative to dosing on Day 1. Meals/snacks on Day -1 must be timed such that there is at least an Meals/snacks will be provided on all days while inpatient as per Section 5.3.2. While inpatient, meal and snack times should match nominal time of 8 hour fast prior to collection of the pre-dose PK sample on Day 1 (see Section 5.3.2). þ.
- Dosing will occur within approximately 10 minutes of completion of breakfast on Day 1. . ـ:
- Safety related laboratory tests may be collected on Day -1 at investigator discretion. If performed, results must be reviewed prior to dosing and must reflect the participant to be in stable medical condition. Total bile acids, lipase, and amylase at Screening only.
- Samples collected at Time 0 on Day 1 must be collected pre-dose. ۲.
- eGFR determination will be performed by the laboratory using the 2021 CKD-EPI Scr-Scys combined equation, as described in Section 4.1 and Appendix 7.
 - If not collected on the designated collection day, collect at the next available time point when biospecimens are being collected in conjunction with participant visit. Ħ.
- Blank pre-dose urine sample to be collected within 24H prior to dosing. Urine should be collected at intervals of 0-6, 6-12 and 12-24 hours after dosing. See Section 8.5.3. If participant is on dialysis and has no urine output, no urine PK samples will be collected 'n.
- For a participant on dialysis who is anuric only, an alternative method (eg, saliva) for urine drug testing may be used o.
- For a participant on dialysis who is anuric only, urinalysis is not required to be collected.
- Test result must be reviewed and deemed acceptable (ie, negative) to continue participation in the study. For a participant on dialysis who is anuric only, an alternative method (eg, blood) for pregnancy testing may be used. ф.

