- 2. Multiply this eGFR value by each participant's ratio of BSA/1.73 to obtain the **BSA-unnormalized** eGFR value as shown below:
 - eGFR (mL/min) = eGFR (mL/min/1.73 m^2) * [BSA (m^2) / 1.73]

The BSA of an individual will be calculated using the following equation:⁶

• BSA $(m^2) = [Weight(kg)^{0.425} \times Height(cm)^{0.725}] \times 0.007184$

The average of the 2 BSA-unormalized eGFR values from Screening visits S1 and S2 will be used for study enrollment and group placement using the categories presented in Table 1. Participants who are not on dialysis must have stable renal function to enter the study, defined as ≤25% difference between 2 measurements of BSA-unnormalized eGFR obtained from the 2 Screening visits, S1 and S2 as listed in the SoA. Visit S2 is optional for participants on dialysis, who will be placed in Group 4 regardless of eGFR value.

Staged Enrollment of Study Groups

- Participants will be dosed in a staged manner such that those with moderate and severe renal impairment (Groups 3 and 4) will be enrolled first.
- Recruitment of participants with mild renal impairment (Group 2) will initiate when approximately 50% of the participants in Groups 3 and 4 have been dosed.

Approval from the sponsor is *required before* proceeding with recruitment for Group 2.

- An average value for age and weight for Groups 2, 3, and 4 will be determined and participants in Group 1 will be recruited to match the average demographics (at a minimum, age and weight, and as much as practically possible gender) across the pooled Groups 2-4.
- Therefore, recruitment of participants without renal impairment (Group 1) may start when approximately 75% of total participants across Groups 2-4 (ie, approximately 17-18 participants) have been dosed.

Approval from the sponsor is *required before* proceeding with recruitment for Group 1.

Refer to Section 1.2 for the Study Schema. For individual participants, the total study duration from Screening visit S1 to the Follow-up contact will be a minimum of approximately 6 weeks and a maximum of up to approximately 10 weeks. The study consists of an initial screening period of up to 28 days, a 7-day inpatient stay at the CRU which includes administration of a single oral dose of PF-07081532, and a follow-up contact (or site visit, per discretion of the PI) that will occur 28-35 days after PF-07081532 administration on Day 1.

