2.1. Modifications to the Analysis Plan Described in the Protocol

Not Applicable

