Appendix 1. Statistical Methodology Details

```
An example of SAS code for ANOVA:
proc mixed data = tab.pk;
       class group;
       model l&var = group /residual;
       lsmeans group/diff cl alpha=0.1;
       ods output lsmeans = lsmeans&var;
       ods output diffs=diffs&var;
run;
An example of SAS code for the PROC REG code for linear regression analyses:
proc reg data=tab.pk;
       model l&var=clcr/clb alpha=0.1;
       ods output ParameterEstimates = param&var;
       ods output FitStatistics = fit&var;
       ods output ANOVA = reg\&var;
run;
An example of SAS code for stepwise regression with model selection using AIC:
proc glmselect data=tab.pk analysis plot=ALL;
       class gender
  model pk p = eGFR age weight gender/ selection=stepwise (select = AIC stop = AIC)
       include=1 hierarchy=none showpvalues;
run;
```

Appendix 2. Categorical Classes for ECG and Vital Signs of Potential Clinical Concern Categories for QTcF

Absolute value of QTcF (msec)	>450 and ≤480	>480 and ≤500	>500
Increase from baseline in QTcF (msec)	>30 and ≤60	>60	

Categories for PR and QRS

PR (ms)	max. ≥300	
PR (ms) increase from baseline	and max. ≥25%	Baseline ≤200 and max. ≥50% increase
	increase	
QRS (ms)	max. ≥140	
QRS (ms) increase from baseline	≥50% increase	

Categories for Vital Signs

Systolic BP (mm Hg)	min. <90	
Systolic BP (mm Hg) change from baseline	max. decrease ≥30	max. increase ≥30
Diastolic BP (mm Hg)	min. <50	
Diastolic BP (mm Hg) change from baseline	max. decrease ≥20	max. increase ≥20
Seated pulse rate (bpm)	min. <40	max. >120

Measurements that fulfill these criteria are to be listed in the report.

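### SAP 3.3.4 omits the unit and the BSA/1.73 step, leaving two eGFR scales for the PK regression and for plots whose cut-off lines are in mL/min

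*SAP*

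**What the plan says.** **Protocol 4.1** computes the combined-equation eGFR in mL/min/1.73 m² and then instructs: "Multiply this eGFR value by each participant's ratio of BSA/1.73 to obtain the" unnormalized value, in mL/min. Group placement uses the average of the two screening values on that scale. Protocol Table 1 and SAP Table 2 give the 90, 60 and 30 cut-offs in mL/min, and a footnote to each table calls the value unnormalized.

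**SAP 3.3.4** states: "For reporting purposes, eGFR will be calculated using the 2021 CKD-Scys formula". It prints the combined equation with no output unit and no BSA term. The three exploratory equations below it are all labelled per 1.73 m².

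**SAP 6.1.1.2** says the regression may use "renal function (eGFR), calculated using the 2021 CKD-EPI Scr-Scys Combined equation given in Section 3.3.4". It then commits to plots of PK parameters against baseline renal function ("eGFR as obtained on Day 1) will be constructed") and adds: "Vertical lines for the renal function group cut-off values will also be presented on the plots".

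**Schedule of Activities footnote (protocol 1.3)** on eGFR reads: "eGFR determination will be performed by the laboratory using the 2021 CKD-EPI Scr-Scys combined equation, as described in Section 4.1 and Appendix 7".

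**SAP 2.1**, headed "Modifications to the Analysis Plan Described in the Protocol", is marked not applicable.

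**The concern.** A programmer who follows SAP 3.3.4 as written produces eGFR in mL/min/1.73 m². The cut-off lines on the plots are in mL/min. Because BSA differs between participants, relabelling the axis cannot repair the mismatch: each point moves by its own factor.

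The regressed outcomes are absolute clearances. Protocol Table 2 gives CL/F as Dose/AUCinf, and Table 3 gives CLr as Ae24/AUC24; neither is per 1.73 m². The mL/min scale therefore matches both the outcomes and the groups, and the indexed scale matches neither.

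At stake is the reading of the supplementary figures and of any regression of clearance on renal function. A large participant enrolled as having normal renal function could appear on the impaired side of the 90 line.

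**Working it through.** **Can the text settle the scale?**

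- The Schedule of Activities footnote cites both protocol 4.1 (which has the BSA step) and Appendix 7 (which does not). It points towards mL/min, and the plot sentence in SAP 6.1.1.2 can be read through it.
- Footnote h of protocol Table 5 cites Appendix 7 alone, which points towards the indexed value.
- Protocol 4.1 words the BSA step for the two screening visits. The regression and plots use Day 1.
- The SAP cites protocol 4.1 only for categorisation at screening (SAP 2.3).
- Protocol 9.3.2.3 names no scale.
- The example code in SAP Appendix 1 uses "model l&var=clcr/clb alpha=0.1" in one block and `eGFR` as regressor in another.

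The passages point to two scales and none decides between them.

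**How far apart are the scales?** The formulas are those of protocol 4.1: BSA = W^0.425 × H^0.725 × 0.007184; factor = BSA/1.73; indexed value = mL/min value ÷ factor. The entry limits are weight above 50 kg and BMI 17.5 to 45.4 (protocol 5.1.1). The documents set no height limit, so the heights are illustrative.

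| Body size | BSA (m²) | Factor | 90/60/30 mL/min on the indexed scale |
|---|---|---|---|
| 50.6 kg, 170 cm (BMI 17.5) | 1.576 | 0.911 | 98.8 / 65.9 / 32.9 |
| 90 kg, 170 cm | 2.014 | 1.164 | 77.3 / 51.5 / 25.8 |
| 100 kg, 175 cm | 2.151 | 1.243 | 72.4 / 48.3 / 24.1 |
| 131.2 kg, 170 cm (BMI 45.4) | 2.364 | 1.366 | 65.9 / 43.9 / 22.0 |

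The eligible factor range is 0.848 to 1.181 at 155 cm and 1.041 to 1.561 at 185 cm. At 170 cm the two scales agree only at 63.0 kg (BMI 21.8).

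**Within Group 1.** Matching allows ±15 kg around the pooled mean (protocol 5.1.2). Two participants, both at 95 mL/min and 170 cm, would plot on the indexed scale as follows:

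- Assumed mean 80 kg: 93.7 (at 65 kg) and 79.8 (at 95 kg).
- Assumed mean 90 kg: 88.2 (at 75 kg) and 76.4 (at 105 kg).
- Assumed mean 100 kg: 83.6 (at 85 kg) and 73.5 (at 115 kg).

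**How many points would fall outside their own band?** This was simulated with 200,000 draws per group. Every input is an assumption: uniform eGFR within bands, a normal-band ceiling of 110-140 mL/min, mean BSA 1.73-2.2 (SD 0.2), and Day 1 variation of 8-12%. On the mL/min scale 9-17% cross a line; on the indexed scale 15-42% do. The excess is 1.4 to 9.7 of 32 points and depends mainly on mean BSA.

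**Effect on the regression.** This used 4,000 simulated trials of n = 32, with log clearance linear in mL/min eGFR, a 1.5-fold difference between 105 and 20 mL/min, residual SD 0.4 and mean height 170 cm.

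| Assumed mean weight | Normal-versus-severe log contrast, mL/min → indexed | R² | Slope ratio |
|---|---|---|---|
| 75 kg | 0.402 → 0.390 (-3.0%) | 0.158 → 0.154 | 1.035 |
| 90 kg | 0.403 → 0.388 (-3.7%) | 0.157 → 0.153 | 1.107 |
| 100 kg | 0.409 → 0.393 (-3.9%) | 0.160 → 0.154 | 1.152 |

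A variant that assumed BSA directly gave a 4-5% fall in the contrast. The slope ratio is mostly a change of unit.

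**Cockcroft-Gault label.** SAP 3.3.4 labels the result per 1.73 m², but the printed formula is proportional to weight and has no indexing step. For a man of 60 with creatinine 1.2 mg/dL:

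- 60 kg: (80 × 60)/(72 × 1.2) = 55.6.
- 120 kg: (80 × 120)/(72 × 1.2) = 111.1.

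The label does not fit the formula.

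**The case against.** The strongest reply is that the documents, read together, favour mL/min. SAP 3.3.4 is silent on the unit, and protocol 4.1, the only place that states the combined equation's output unit, applies the BSA step at once. The SAP's cut-offs are unnormalized, SAP 2.1 declares no departure from the protocol, and the plot sentence does not cite 3.3.4. On this view the gap is a missing cross-reference. That is a fair reading and probably the intended one. But 3.3.4 sets a rule for reporting and the regression is sent to it by name, so a literal reader reaches the other scale.

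It is also true that little depends on the outcome. The regression is optional, no hypothesis test or decision rule applies, plotting symbols identify each participant's group, and the primary ANOVA is unaffected. Even on the mL/min scale some points cross the lines, because groups use screening averages and the plots use Day 1, and dialysis participants enter Group 4 whatever their eGFR. The crossing counts rest on assumed inputs and show only a possible range. All of this stands; it limits the severity without removing the conflict.

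The regressor name sits in example code and carries little weight. The Cockcroft-Gault label is a real error, but it concerns an exploratory equation only.

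**Conclusion.** The point holds. As written, the SAP's eGFR rule and its cut-off lines are on different scales, and no passage fixes which applies on Day 1. The size of the gap follows from the protocol's own BSA formula and entry limits: a participant-specific factor of 0.91 to 1.37 at 170 cm, wider across other heights. That is enough to move individual points across a cut-off line.

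The inferential effect is small: roughly 3-5% on the normal-versus-severe contrast and a negligible change in R², under assumed weights and a clearance relation linear in mL/min. The consequence is confined to supplementary and exploratory output. It should be corrected before programming, but it does not threaten the primary result.

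**What to change.** Add to SAP 3.3.4, in substance: *The combined-equation result (mL/min/1.73 m²) is multiplied by BSA/1.73, with BSA computed from the S1 height and weight by the formula in protocol 4.1. This value, in mL/min, is used for Sections 5.2.4 and 6.1.1.2 and for every plot with cut-off lines.* Naming S1 matters because height and weight are measured only then.

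Also:

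- Use one regressor name in the Appendix 1 code.
- For the exploratory equations of SAP 6.1.1.3, state the scale. Convert the creatinine-only CKD-EPI and MDRD values to mL/min if they are compared with the main regression or the cut-offs.
- Correct the Cockcroft-Gault unit label so that nobody applies a BSA conversion to it.

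The cost is SAP wording and one derivation line. It needs no new data and changes neither the groups nor the primary analysis.
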